6.2.2 Blinding procedures

As described in 6.1, patients will receive 15 sessions of rTMS over the left SMA in a blinded fashion. They will not be able to see which protocol is used (coil placement on top of their head, machine display behind the patients). Because of the parallel arm design, they will not know how the other protocols feel. Patients will be eye-blinded and ear-plugged during rTMS.

The teams performing assessments and rTMS stimulations will be strictly distinct. Therefore, patients and outcome assessors will be blinded to treatment arm.

6.2.3 Other methods of minimising bias

Outcomes are assessed with instrumental means or validated questionnaires. All assessments will follow a standard routine. Assessors will be trained to use instruments by the PI.

6.3 Unblinding Procedures (Code break)

In case of severe adverse events, an unblinding can take place at the responsibility of the principal investigator. In this case, the participant will not be able to further participate in the study. The allocated intervention order will be kept in a sealed envelope. The sealed envelopes will be stored at a central place, i.e. the office of the lab, so they can be accessed in case of any emergency.

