5. STUDY OUTCOMES

5.1 Primary Outcome

The primary outcome variable is the SRRS score as a surrogate marker of psychomotor slowing. The primary endpoint will be the change SRRS ratings from baseline to week 3 measured with the SRRS⁹². The SRRS is administered at baseline, week 1, week 2, week 3, week 6, and week 24. It is an observer rated scale quantifying the severity of psychomotor slowing with 15 items, each ranging 0-4. The SRRS has been developed to target this behavior and has been used in previous trials. Assessments will be performed by blinded raters, who have been trained to use the scale reliably.

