8.3 Dose / Device modifications

In case of intolerable side effects, the study will be discontinued for the participant. No dose or device modifications are planned.

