8.5 Data Collection and Follow-up for withdrawn participants

If participants withdraw their consent, they will be contacted immediately to clarify whether there were intolerance issues with the study. See section 9.2.5 for safety follow-up measures. In case of withdrawal the data will be analyzed and stored encrypted as all the data of the other participants. However, we will remove the encryption key for the participants who withdrew consent and therefore it will not be possible to identify the subjects from encrypted data. Patients who withdrew consent will be invited for the 6 month follow-up interview using their preferred way of contact (Email, letter).

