9.2.4.3 Vital signs

No routine measurement of vital signs is planned. If patients report dizziness, clinical routines will include measurement of blood pressure and heart rate.

9.2.5 **Assessments in participants who prematurely stop the study**

Participants who prematurely stop the study will be immediately assessed for adverse events. In case of adverse events reports, a physical examination will be conducted and results will be recorded accordingly. Follow-up examinations will be planned within the next 14 days in case of continuing problem related to adverse events, and these examinations will be continued every 14 days until the health issue is resolved.

9.3 **Procedures at each visit**

9.3.1 **Screening visit**

- Check the inclusion and exclusion criteria, use CRF
- Collect demographic data, use CRF
- Conduct urine pregnancy test in female participants between 18 and 50 years of age
- Assess diagnoses with SCID, document results in CRF
- Assess handedness with EHI¹⁰¹, document result in CRF
- Assess medical history in CRF

See table study events at 9.1

9.3.2 **Visit 2 (baseline, week 0)**

- Assess current psychopathology, use PANSS interview and BNSS, document in CRF
- Assess formal thought disorder, use TALD interview, document in CRF
- Assess Neurological soft signs, use NES, document in CRF
- Assess psychiatric history with CASH interview in patients, document result in CRF
- Assess primary outcome with SRRS scale, document in CRF
- Assess motor behaviour with rating scales, use BFCRS, UPDRS, AIMS, document results in CRF
- Assess functioning, use GAF, SOFAS, and UPSA-brief, document results in CRF
- Hand out self-rating questionnaires SNS and IPAQ, collect and document in CRF
- Conduct coin rotation test, record on video
- Record gross motor activity using actigraphy
- Test cortical excitability using the TMS device according to standard procedure. Record electronic data
- Acquire MRI scans at University Institute of Diagnostic and Interventional Neuroradiology
- Acquire posturography at University Hospital, Dept. of Neurology, record electronic data
- Record current medication regime in CRF
- Schedule 5 rTMS sessions
- Schedule next visit

9.3.3 **Visit 3 and 4 (week 1 and 2)**

- Assess primary outcome with SRRS scale, document in CRF
- Assess side effects with questions in the CRF
- Record current medication regime in CRF
- Schedule 5 rTMS sessions
- Schedule next visit

9.3.4 **Visit 5 (end of intervention, week 3)**

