10.1.3 Follow up of (Serious) Adverse Events

If adverse events occur, patients are followed-up with extra-visits after 14 days until the issue has resolved. This applies to patients who continue with the study but also to patients who prematurely exit the study. In case subjects are lost to followed-up, study personnel will contact the treating psychiatrists (or if unavailable, the general practitioners) in order to inform on serious adverse events and the recommendations for follow-up clinical examinations. In cases of headaches for example, care would include the prescription of a non-steroidal antirheumatic drug, i.e. pain medicine, according to the person's preferences, medical history, or interaction with existing medication.

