11.4 Planned Analyses

11.4.1 Datasets to be analysed, analysis populations

All data from subjects in the intent-to-treat population, who received at least one dose of rTMS will be used in the analyses of rTMS effects. We will conduct sensitivity analyses in all trial-completers (see 11.5).

In the analyses on biological and clinical correlates of PS, we will use all data of the baseline assessment, thus including data from subjects who dropped-out prior to the first rTMS session.

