11.5 Handling of missing data and drop-outs

We will apply the last-observation-carried-forward (LOCF) method in the final analyses. In case a patient withdraws consent before the first rTMS stimulation, we will recruit an additional patient. The number of all patients recruited and randomized will be reported in the publications.

Sensitivity analyses will be performed in order to establish whether premature dropout would influence the results. Therefore, the primary analyses will be repeated with all subjects who completed the interventional trial. Further tests will establish whether drop-outs differ from completers in basic clinical or demographic variables.

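### Code breaks and intolerable side effects end study participation, not just stimulation, so no week 3, 6 or 24 outcome assessment is planned for these still-consenting patients

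*Combined protocol and SAP*

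**What the plan says.** Two rules take a patient out of the study for safety reasons without any withdrawal of consent. Section 6.3 allows the principal investigator to break the code after a severe adverse event and then states: "In this case, the participant will not be able to further participate in the study". Section 8.3 states: "In case of intolerable side effects, the study will be discontinued for the participant".

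Safety follow-up after an early stop is provided for. Section 9.2.5 says: "Participants who prematurely stop the study will be immediately assessed for adverse events". It adds a physical examination if events are reported, and examinations every 14 days until resolution. Section 10.1.3 repeats the follow-up and says of it: "This applies to patients who continue with the study but also to patients who prematurely exit the study". Section 7.4 refers to the same examinations.

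The only outcome contact for early leavers is in 8.5: "Patients who withdrew consent will be invited for the 6 month follow-up interview using their preferred way of contact".

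On analysis, 11.4.1 keeps the data of intention-to-treat patients "who received at least one dose of rTMS will be used in the analyses of rTMS effects". Section 11.5 fills missing values by LOCF. Its sensitivity analysis is in completers: "Therefore, the primary analyses will be repeated with all subjects who completed the interventional trial".

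**The concern.** Stopping a treatment and stopping observation are separate decisions. After a code break or intolerable stimulation there is good reason to stop rTMS, but a patient who still consents can usually still be rated. The plan joins the two decisions, so obtainable outcomes are replaced by imputed ones in patients selected by their safety experience.

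The primary endpoint, change in SRRS to week 3, is affected if the exit comes before week 3. The rating scales behind hypotheses 1a, 4a and 4b are affected more, because they are not rated between baseline and week 3. Neither the LOCF analysis nor the completer analysis uses these patients' true later outcome, and nothing will have been collected against which to check the imputation afterwards.

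Exposure also differs by arm. The waiting group receives no stimulation before week 3, so an exit under 8.3 cannot cost it the primary endpoint. The placebo coil emits no magnetic pulse, so intolerance could plausibly differ between the real and placebo coils as well.

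**Working it through.** **Is there any text that restores the visits?** Each relevant section was read for what it plans after an exit under 6.3 or 8.3 in a patient who still consents.

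| Section | What it plans after the exit | Outcome rating at week 3, 6 or 24? |
|---|---|---|
| 7.4 | Adverse event examinations; use of data already collected | No |
| 8.5 | 6-month interview, for those who withdrew consent | Not stated for these patients; weeks 3 and 6 not covered for anyone |
| 9.2.5 | Adverse event check, physical examination, 14-day follow-up | No |
| 10.1.3 | Extra safety visits until resolution | No |
| 11.4.1, 11.5 | Retention in the analysis, LOCF, completer analysis | No (analysis only) |

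Read literally, a patient who withdraws consent is invited back at 6 months, while a consenting patient removed for safety is not.

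**Ratings lost per patient, groups 1-3.** Section 5.1 gives the SRRS schedule: "The SRRS is administered at baseline, week 1, week 2, week 3, week 6, and week 24". That is 6 ratings. The PANSS, BNSS, UPDRS, BFCRS and AIMS are rated at weeks 0, 3, 6 and 24 (9.1.1), which is 4 ratings.

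| Exit before the visit at | SRRS obtained | SRRS lost | Other scales obtained | Other scales lost |
|---|---|---|---|---|
| Week 1 | 1 | 6 - 1 = 5 | 1 | 4 - 1 = 3 |
| Week 2 | 2 | 6 - 2 = 4 | 1 | 3 |
| Week 3 | 3 | 6 - 3 = 3 | 1 | 3 |

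On the other scales only baseline remains, so the LOCF change is baseline minus baseline = 0 at weeks 3, 6 and 24.

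**Patients exposed for the primary endpoint.** Three arms are stimulated from week 0, so an 8.3 exit can cost the week 3 SRRS in 3 x 22 = 66 of 88 patients. This counts patients at risk; it does not estimate how many will leave.

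**The plan's own figure.** The 22 per arm reproduces as the group-by-time test in 11.2: noncentrality = 0.23² x 88 x 2 / (1 - 0.5) = 0.0529 x 88 x 2 / 0.5 = 18.6, with 3 and 84 degrees of freedom. Power is 0.957, and 88 is the smallest multiple of 4 that reaches 0.95. The figure contains no allowance for lost week 3 values.

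**Effect on an arm's mean change.** Suppose k of 22 patients exit before week 3 and would otherwise have had the arm's average change D. With zero imputed for those k, the arm mean becomes D x (22 - k)/22, a shrinkage of k/22. The documents give no exit rate, so k = 1, 2 and 3 are assumptions:

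- k = 1: 1/22 = 4.5%
- k = 2: 2/22 = 9.1%
- k = 3: 3/22 = 13.6%

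These percentages apply to the scales without weekly ratings. For SRRS, LOCF carries a week 1 or week 2 score unless the exit falls in the first week, so no single shrinkage figure applies.

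**The case against.** The strongest counter-text is 8.5. Its heading refers to withdrawn participants in general, and 7.4 uses the word withdrawal for adverse event exits too. It would be odd to invite back those who withdrew consent and not those who still consent. A generous reading could therefore extend the week 24 invitation to these patients. That makes week 24 partly a matter of unclear drafting, but weeks 3 and 6 remain uncovered on any reading.

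The triggers are also narrow. Unblinding is discretionary and tied to severe events. The sponsor's prior trial with the same stimulation protocol had one serious adverse event, unrelated to the intervention (3.7), and the typical effects listed in 10.1 are mild. This stands, and it is why the numbers are expected to be small.

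SRRS is rated weekly, so the primary endpoint is better protected than the other scales; this also stands. The zero-change result comes from LOCF and would affect any dropout, but here the missing values are created by rule. Section 11.5 also compares drop-outs with completers on basic clinical and demographic variables. That may show selective dropout, but it recovers no outcomes.

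Finally, ratings of an unblinded patient may carry expectation bias. This is a reason to flag such ratings. It does not apply to 8.3 exits without a code break, and the raters, who are separate from the stimulation team (6.2.2), need not learn the allocation.

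**Conclusion.** The concern holds. As written, 6.3 and 8.3 end observation as well as stimulation, and no other section schedules outcome ratings for patients who leave by these routes and still consent. Per patient in groups 1-3, an exit before week 3 loses 3 to 5 of 6 SRRS ratings and 3 of 4 ratings on the other clinical and motor rating scales. The shrinkage of 4.5% to 13.6% in an arm's mean change on those scales rests on assumed exits of 1 to 3 of 22 and on average change in the patients who leave.

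The direction of any bias is unknown. A carried early score understates change in a patient who would have improved and hides worsening in one who would have worsened. The frequency cannot be estimated from the documents and is probably low. This should be changed because the change is cheap; it does not by itself undermine the primary comparison.

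**What to change.** In 6.3, replace the removal sentence. State that the code is disclosed only to those who need it for the patient's care, that raters (and the patient where possible) stay blind, and that the patient is asked to attend the scheduled week 3, 6 and 24 assessments unless consent is withdrawn. In 8.3, state that intolerable side effects end stimulation, not study participation, and that the same assessments are kept. For the waiting group, use its own schedule: weeks 6, 9 and 24.

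The same wording would suit two similar exits: non-compliance (8.4) and discontinuation at the treating physician's request after deterioration (7.4).

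The core change is two sentences of protocol text, and the visits are already scheduled for these patients. The downside is that some patients will decline, and ratings made after a patient has been unblinded must be flagged.

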7. STUDY POPULATION

The aim is to test 88 subjects with schizophrenia spectrum disorders and 40 healthy control subjects. Both genders will be included, age range 18 – 65 years.

7.1 Eligibility criteria

Participants fulfilling all of the following **inclusion** criteria are eligible for the study:

- ages 18–60 years
- Right-handed subjects
- Ability and willingness to participate in the study
- Ability to provide written informed consent
- Informed Consent as documented by signature (Appendix Informed Consent Form)

- **Patients only:** schizophrenia spectrum disorders according to DSM-5 **with** psychomotor slowing (SRRS score ≥ 15)

The presence of any one of the following **exclusion** criteria will lead to exclusion of the participant:

- Substance abuse or dependence other than nicotine
- Past or current medical or neurological condition associated with impaired or aberrant movement, such as brain tumors, stroke, M. Parkinson, M. Huntington, dystonia, or severe head trauma with subsequent loss of consciousness.
- Epilepsy or other convulsions
- History of any hearing problems or ringing in the ears
- Standard exclusion criteria for MRI scanning and TMS; e.g. metal implants, claustrophobia
- Patients only: any TMS treatment in the past 3 months
- Women who are pregnant or breast feeding,
- Intention to become pregnant during the course of the study,
- Female participants who are surgically sterilised / hysterectomised or post-menopausal for longer than 2 years are not considered as being of child bearing potential.
- Previous enrolment into the current study,
- Enrolment of the investigator, his/her family members, employees and other dependent persons
- **Controls only:** history of any psychiatric disorder or first-degree relatives with schizophrenia spectrum disorders.

7.2 Recruitment and screening

Healthy participants will be recruited by word-of-mouth, an internet link at the homepage of the department and flyers at supermarkets or at the University of Bern. Staff of the University Hospital of Psychiatry Bern will not be recruited. Furthermore, patients will be asked for participation at the inpatient and outpatient departments of the University Hospital of Psychiatry, Bern. All participants will spend approximately a total of 18 hours in the study on 7 different assessment days (screening, baseline, 3x during interventions and 2 follow-ups). Thus, they will be compensated by a single payment of CHF 200,-. Screening is described in section 9.1 and performed by master-level psychologists or psychiatrists.

7.3 Assignment to study groups

Randomization procedure is described in section 6.2.1. When the investigators have recruited a patient-participant, the principal investigator will allocate the person to a study group based on the randomization list and the sequence of enrolment in the study. From the list of numbers, patients are sequentially allocated by the principal investigator to one of the four treatment arms. The principal investigator will provide written information to the investigators concerning the treatment arm. The lists with the group allocations are only accessible for the principal investigator.

7.4 Criteria for withdrawal / discontinuation of participants

Participants may discontinue the trial at any time or withdraw consent. Furthermore, the treating physicians may request study discontinuation in case of significant deterioration of the condition at any time during the intervention period. All data from subjects in the intent-to-treat population, who received at least one dose of rTMS will be further used in the analyses. We will apply the last-observation-carried-forward (LOCF) method in the final analyses. In case a patient withdraws consent before the first rTMS stimulation, we will recruit an additional patient. The number of all patients recruited and randomized will be reported in the publications. All data from neuroimaging acquisition and motor behaviour will be used whenever possible, e.g. for analyses of baseline associations between brain imaging and behavior. In case of withdrawal due to adverse events or serious adverse events there will be follow-up examinations after 14 days and repeatedly until the problem is resolved, see 9.2.5.

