Measurements and procedures:	Participants will be screened and randomized to one of four arms before baseline assessments. Intervention period will be three weeks. Each week the primary outcome variable and safety will be assessed. At baseline and end of intervention (week 3), patients will be assessed with clinical and motor rating scales, tasks assessing fine and gross motor behaviour, TMS measures of cortical excitability, posturography, MRI neuroimaging, and tests of social and community functioning. Follow-ups will be conducted at week 6 and 24 including clinical and motor measures, cortical excitability, and social and community functioning. For cross-sectional comparisons of cortical excitability and neuroimaging, a group of 40 healthy control subjects matched for age, gender, and education, will be tested longitudinally with neuroimaging, motor tests, cortical excitability and posturography at baseline and week 3. Controls will not receive any intervention.
Study Product / Intervention:	low-frequency rTMS has inhibitory effects on brain function. We will apply 1'000 pulses at 1 Hz over the left SMA at an intensity of 110% of the resting motor threshold (approximate duration 17 minutes) in a total of 15 daily sessions (5 per week)

Control Intervention (if applicable):	
Active control: Intermittent theta burst (iTBS) enhances local brain activity. We will apply 600 pulses at 50 Hz (stimulation in 2 sec trains every 10 sec for 190 sec in total) over the left SMA at an intensity of 80% of the resting motor threshold. iTBS will be repeated after 15 min totaling to 1200 pulses per session in a total of 15 daily sessions (5 per week).
 
Placebo control: We will use a placebo-coil that looks identical to the real one and makes identical noises. Stimulation parameters are the same as in the active intervention, except that no magnetic pulse is emitted. Thus, placebo coil will be placed over the left SMA with 1000 clicks at 1 Hz (approximate duration 17 minutes) in a total of 15 daily sessions (5 per week).
 
Waiting list: This group will have baseline measures at baseline and week 3 and receive the active protocol from week 3 to week 6.

Number of Participants with Rationale:	
Number of participants in the intervention: 88 patients (22 per protocol arm). In addition, to complement neuroimaging and neurophysiological analyses (no intervention) we will include 40 healthy control subjects matched for age, gender, and education.

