6.2 Methods of minimising bias

6.2.1 Randomisation

Using the free software research randomizer, we will generate for the patients a list with four numbers indicating the group allocation, i.e. stimulation types. Allocation will be 1:1:1:1 across the whole intended sample. Subsequent numbers of study inclusion will therefore determine to which study arm the patient will be randomized. The lists will only be available for the principal investigator and locked in his office. He will perform randomization and give the written group allocation to the investigators.

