8.1.2 Control Intervention (standard/routine/comparator treatment / medical device)

All stimulations are delivered with the same device. The stimulation sites are the same (left SMA) for all groups. The iTBS protocol is shorter (3 mins), the placebo protocol will be delivered with a specific placebo-coil that looks identical, makes identical sounds but produces no magnetic pulses.

Placebo control: 1 Hz stimulation of 17 mins over left SMA without magnetic emission, 15 sessions in total (5 per week)

Active control: iTBS stimulation over left SMA, 21 mins per session, 15 sessions in total (5 per week)

Waiting list: no intervention during the first three weeks, afterwards active stimulation: 1 Hz stimulation of 17 mins over left SMA, 15 sessions in total (5 per week)

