9. STUDY ASSESSMENTS

9.1 Study flow chart(s) / table of study procedures and assessments

Flow charts are distinct for controls and patients, because controls receive no intervention. Furthermore, three patient groups will start interventions immediately (lf-rTMS, iTBS, and Placebo; i.e. groups 1-3), but one group will be waiting for 3 weeks and then enter the intervention phase (waiting group; i.e. group 4).

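### Replacing patients who withdraw before the first rTMS covers only the baseline work-up in groups 1-3 but the whole primary period in the waiting arm, and the allocation of replacements is not defined

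*Combined protocol and SAP*

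**What the plan says.** Section 7.4, repeated in 11.5, states the replacement rule: "In case a patient withdraws consent before the first rTMS stimulation, we will recruit an additional patient". Neither section says which list number or arm that patient receives.

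The first stimulation falls at different times. Section 9.1 says "three patient groups will start interventions immediately (lf-rTMS, iTBS, and Placebo; i.e. groups 1-3" and treats the waiting group separately; the schedule in 9.1.1 marks randomisation and the first rTMS at the same week-0 visit. Section 8.1.2 describes the fourth arm: "Waiting list: no intervention during the first three weeks, afterwards active stimulation: 1 Hz stimulation of 17 mins over left SMA". In 9.1.2 its first sessions are listed at the week-3 visit, after that visit's SRRS. The synopsis puts randomisation ahead of baseline: "Participants will be screened and randomized to one of four arms before baseline assessments".

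On the endpoint, 5.1 says "The primary endpoint will be the change SRRS ratings from baseline to week 3 measured with the SRRS". The waiting arm is one of the four groups in the primary ANOVA (11.4.2).

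On the analysis set, 11.4.1 says "All data from subjects in the intent-to-treat population, who received at least one dose of rTMS will be used in the analyses of rTMS effects". Dropouts are handled by LOCF (7.4, 11.5).

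On allocation, 6.2.1 says "Allocation will be 1:1:1:1 across the whole intended sample" and 7.3 says "From the list of numbers, patients are sequentially allocated by the principal investigator to one of the four treatment arms". List length, blocks and spare numbers are not stated. Only the principal investigator holds the list.

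**The concern.** The trigger is tied to the first stimulation, an event that comes before the primary period in three arms and after it in the fourth. One sentence therefore works as two rules. Two patients who leave in week 2 are handled in opposite ways: the one in groups 1-3 is kept and not replaced, while the one in the waiting arm is replaced and, having no dose, is left out of the analysis of rTMS effects.

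Waiting-arm patients know their allocation (6.1 says this group is not completely blinded), so withdrawal during the wait could depend on how they are doing. If those who fail to improve leave more often, the remaining patients show too much spontaneous improvement. Estimating that improvement is what the arm is for: Aim 3, and the waiting-list versus placebo comparison among the synopsis outcomes.

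The second gap is allocation. The person who holds the list also allocates, and may run optional interim analyses of the primary outcome with the team (11.4.4). Where a replacement goes should not be left open.

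**Working it through.** **1. The plan's own figure.** Inputs from 11.2: f = 0.23, correlation 0.5, alpha 0.05, power 0.95, 4 groups, 2 time points. For the group-by-time interaction, lambda = N × m × f² / (1 − rho) = 88 × 2 × 0.0529 / 0.5 = 18.62, with 3 and 84 degrees of freedom. Power is 0.957. The smallest N is 86, which becomes 88 with equal groups, so the stated 88 is reproduced. At 84 (21 per arm) power is 0.947. The calculation contains no allowance for loss, which gives a motive to keep 22 per arm, but losing one patient per arm costs only 0.957 − 0.947 = 0.010.

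**2. Unequal windows.** Assumptions, not in the documents: the same weekly withdrawal hazard h in every arm (2%, 5% or 10%), and a window of d = 1, 3 or 7 days in groups 1-3. The waiting-arm window is 3 weeks.

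- Groups 1-3: p = 1 − (1 − h)^(d/7). Waiting arm: p = 1 − (1 − h)³.
- Reading A, vacated arm refilled to 22: expected replacements = 22p / (1 − p).
- Reading B, next list number until 88 are treated: number randomised = 88 / (1 − mean p). Each arm receives a quarter and keeps the fraction 1 − p.

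Example, h = 5% and d = 3: waiting p = 1 − 0.95³ = 0.143; other p = 0.022. Reading A gives 3.66 replacements in the waiting arm and 0.49 in each other arm, a waiting-arm share of 3.66 / (3.66 + 3 × 0.49) = 71%. Reading B gives 92.8 randomised, 19.9 treated in the waiting arm and 22.7 in each other arm.

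Ranges run over d = 1 to 7:

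| h per week | p waiting | p groups 1-3 | A: replacements, waiting / each other arm | A: waiting share | B: randomised | B: treated, waiting / each other arm |
|---|---|---|---|---|---|---|
| 2% | 5.9% | 0.3-2.0% | 1.37 / 0.06-0.45 | 51-88% | 89.5-90.7 | 21.1-21.3 / 22.2-22.3 |
| 5% | 14.3% | 0.7-5.0% | 3.66 / 0.16-1.16 | 51-88% | 91.8-94.9 | 19.7-20.4 / 22.5-22.8 |
| 10% | 27.1% | 1.5-10.0% | 8.18 / 0.33-2.44 | 53-89% | 95.5-102.7 | 17.4-18.7 / 23.1-23.5 |

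Under A, the refilled places are not randomly allocated. Under B, the waiting arm is depleted and numbers beyond 88 are needed.

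**3. Selection through exclusion of undosed leavers.** No true difference, 22 treated per arm, 20,000 simulated trials per scenario, change scores in SD units. Moderate selection: leavers' change averages 0.5 SD worse than the whole arm, so the stayers' mean shifts by 0.5w / (1 − w), where w is the proportion leaving. Extreme selection: exactly the worst patients leave.

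| Waiting arm leaving | Moderate: shift (SD) | Omnibus type I error | Extreme: shift (SD) | Omnibus type I error |
|---|---|---|---|---|
| 5% | 0.03 | 0.051 | 0.11 | 0.061 |
| 10% | 0.05 | 0.049 | 0.20 | 0.086 |
| 20% | 0.12 | 0.064 | 0.35 | 0.186 |
| 30% | 0.21 | 0.094 | 0.50 | 0.403 |

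For waiting list versus sham, the type I error under moderate selection is 0.051, 0.051, 0.071 and 0.110. The shift comes from omitting leavers from the arm mean and does not depend on whether anyone replaces them.

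**The case against.** The best reply starts from 7.3. Patients are allocated by list order, so an additional patient takes the next number whichever arm it names. A reader might infer that the waiting arm will be selectively refilled. The text does not say so, and read literally it leads to depletion. Refilling needs an unstated step, namely steering replacements to the vacated arm to keep 22 per group. This stands, and refilling is only a conditional risk.

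A reader might also infer that the list stops at 88 and that later patients must be placed by hand. That is inference from silence: 6.2.1 gives a ratio and a scope, not a length, and does not exclude spare numbers. What stands is that nothing is specified.

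The scope is limited too. The rule covers consent withdrawal only, not physician-requested discontinuation (7.4) or non-compliance (8.4). Hypothesis 1a compares lf-rTMS with placebo or iTBS, and those three arms share the same short window. The dose condition in 11.4.1 is confined to rTMS effects, so leavers' data might still be used for Aim 3, although 7.4 words the condition more broadly. Finally, all recruited and randomised patients will be reported, which helps transparency but does not restore comparability.

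None of this removes the unequal trigger, or the opposite handling of two patients who leave in the same week.

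**Conclusion.** The point holds as a difference in how the arms are treated, together with a gap in the allocation rules. The unequal window follows directly from the text. That it is short in groups 1-3 is read from the schedule; no number of days is given.

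The effect falls on the omnibus four-group test and on comparisons involving the waiting list. It would be wrong to conclude that lf-rTMS versus placebo or iTBS is biased by this rule.

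The size cannot be fixed from the documents, which give no withdrawal rate, no SRRS standard deviation and no outcome for leavers. Any shift expressed in SRRS points would rest on an invented deficit in leavers. On the assumptions shown, it is small at 5-10% withdrawal with moderate selection (0.03-0.05 SD, type I error about 0.05). It becomes material at 20-30% (0.12-0.21 SD, 0.06-0.09) or under strong selection. This should be corrected because the correction is cheap, but it does not undermine the design.

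**What to change.** - **7.4 and 11.5:** tie replacement to one event with the same timing in all arms, for example withdrawal before the visit-2 baseline SRRS is complete. Do not replace later withdrawals in any arm.
- **6.2.1:** pre-generate the list beyond 88, for example 104 numbers (26 per arm). Give every additional patient the next unused number, never the vacated arm.
- **7.4 and 11.4.1:** keep waiting-arm patients who have a baseline SRRS in the baseline-to-week-3 analysis although they have had no rTMS dose. The simplest wording is one condition for all four arms: randomised, with a baseline SRRS. Without this change the selection remains, whatever is done about replacement.

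One consequence should be written down. The waiting arm has no SRRS between week 0 and week 3 (9.1.2), so under LOCF a patient who leaves during the wait is given zero change. The completer analysis already planned in 11.5 would show how much that matters.

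The cost is wording in four sections and a longer list, made before the first patient. The downside is that arms may end slightly away from 22; step 1 shows this costs little power.
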